5.2 Exclusion Criteria

1. Patients with symptomatic central nervous system (CNS) metastases must have been treated, be asymptomatic, and meet the following at the time of enrollment:
 - a. No concurrent treatment for the CNS disease (e.g. surgery, radiation, corticosteroids ≥ 10 mg prednisone/day or equivalent).
 - b. No progression of CNS metastases on MRI or CT for at least 14 days after last day of prior therapy for the CNS metastases.
 - c. No concurrent leptomeningeal disease or cord compression.
2. Patients with any history of known or suspected autoimmune disease with the specific exceptions of vitiligo, resolved childhood atopic dermatitis, psoriasis not requiring systemic treatment (within the past 2 years) and patients with a history of Grave's disease that are now euthyroid clinically and by laboratory testing.
3. History of prior allogeneic bone marrow, stem-cell or solid organ transplantation.
4. Treatment with any systemic anti-neoplastic therapy, or investigational therapy within the 4 weeks prior to the initiation of study drug administration.
5. Treatment with radiation therapy within 2 weeks prior to the initiation of study drug administration.
6. Treatment with corticosteroids (≥ 10 mg per day prednisone or equivalent) or other immune suppressive drugs within the 14 days prior to the initiation of study drug administration. Steroids for topical, ophthalmic, inhaled or nasal administration are allowed.
7. History of clinically significant cardiovascular disease including but not limited to:
 - a. Myocardial infarction or unstable angina within the 12 weeks prior to the initiation of study drug.
 - b. Uncontrolled hypertension: systolic blood pressure (SBP) > 180 mmHg, diastolic blood pressure (DBP) > 100 mmHg.
 - c. QTcB prolongation > 480 msec.
 - d. Congestive heart failure (New York Heart Association [NYHA] class III-IV)

8. Clinically-significant gastrointestinal disorders including:
 - a. Any history of gastrointestinal perforation unless the affected area has been deemed by the investigator to no longer be a risk for perforation by the investigator.
 - b. History of clinically significant gastrointestinal bleeding within 4 weeks prior to the initiation of study drug.
 - c. History of acute pancreatitis within 4 weeks prior to the initiation of study drug
 - d. Diverticulitis that is clinically significant in the opinion of the Investigator based on the extent or severity of known disease and/or the occurrence of clinically-significant disease flares within 4 weeks prior to the initiation of study drug administration.
9. Evidence of active viral, bacterial, or systemic fungal infection requiring parenteral treatment within 7 days prior to the initiation of study drug. Patients requiring any systemic antiviral, antifungal, or antibacterial therapy for active infection must have completed treatment no less than one week prior to the initiation of study drug.
10. Known positive testing for human immunodeficiency virus or history of acquired immune deficiency syndrome.
11. Known history of hepatitis B or hepatitis C infection or known positive test for hepatitis B surface antigen, hepatitis B core antigen, or hepatitis C polymerase chain reaction (PCR).
12. Second primary invasive malignancy that has not been in remission for greater than 2 years. Exceptions that do not require a 2 year remission include: related non-melanoma skin cancer; cervical carcinoma in situ on biopsy; or squamous intraepithelial lesion on Pap smear; localized prostate cancer (Gleason score < 6); or resected melanoma in situ.
13. History of trauma or major surgery within 4 weeks prior to the initiation of study drug administration.
14. Any serious underlying medical or psychiatric condition that would impair the ability of the patient to receive or tolerate the planned treatment at the investigational site.
15. Known hypersensitivity to recombinant proteins, any excipient contained in the drug or vehicle formulation for MGA271, pembrolizumab or MGA012 (**Section 6.1**).
16. Vaccination with any live virus vaccine within 4 weeks prior to the initiation of study drug administration. Inactivated annual influenza vaccination is allowed.
17. Dementia or altered mental status that would preclude understanding and rendering of informed consent.
18. Employees of MacroGenics, Inc.

19. Prisoners or other individuals who are involuntarily detained.
20. Any issue that in the opinion of the investigator, would contraindicate the patient's participation in the study or confound the results of the study.

5.3 Withdrawal of Patient from the Trial or Study Drug

5.3.1 Guidelines for Permanent Discontinuation

Patients who meet the following criteria should be permanently withdrawn from study therapy. Patients will continue to be followed as appropriate and consistent with protocol guidelines, but should receive no further study therapy with MGA271 or pembrolizumab or MGA012.

- The patient experiences adverse events that necessitate discontinuation of either study drug.
- The Investigator assesses that the patient's safety is adversely impacted by continuing study therapy.
- Uncontrolled intercurrent illness unrelated to cancer that renders continuing study treatment unsafe or regular study visits impossible.
- The Sponsor, Investigator, or Regulatory Agency terminates the study.
- The patient requests to be discontinued from the study, i.e. withdraws consent.
- Noncompliance with study medication or protocol-required evaluations.
- The patient exhibits progression of disease [according to irRC (i.e., irRECIST)].
- If the patient becomes pregnant during the study, the patient must discontinue study treatment immediately. Reports of pregnancy will be requested until delivery or termination in order to monitor the pregnancy outcome.
- A violation of enrollment criteria or other significant protocol violation is discovered after a patient has been enrolled and treated such that continued treatment would not be in the best interests of the patient.

If the Investigator decides that the patient should be withdrawn from the study or from dosing for any reason other than disease progression, the Sponsor or its designee must be alerted within 24 hours via an Immediately Reportable Event form ([Section 7.9](#)).

Patients who withdraw before Study Day 42 for a reason unrelated to drug toxicity may be considered to have inadequate data to support dose escalation. In this case, replacement patients may be enrolled in the same dose level.

Procedures for handling patients who fail to appear for study visits and criteria regarding when to consider patients lost-to-follow-up will be defined in the Study Procedures Manual.

6 STUDY TREATMENTS

6.1 Description of Treatments and Study Drug and Supplies

Study drugs will be administered as an open-label IV solution, followed by observation.

Under no circumstances is the Investigator allowed to release these clinical supplies for use by another physician not named on Form FDA 1572 or to administer study drug to a patient who is not enrolled in this study. Study drug must be dispensed at an institution specified on Form FDA 1572.

Requests to MacroGenics, Inc. for additional study drug should be made at least 2 weeks in advance.

6.1.1 MGA271

The MGA271 drug product is a

MGA271 is supplied as a

administered as an IV push or bolus. MGA271 must not be

6.1.2 Pembrolizumab

Pembrolizumab (marketed as KEYTRUDA by Merck & Co., Inc., Whitehouse Station, NJ 08889 U.S. License No. 1713) is a humanized monoclonal antibody that blocks the interaction between PD-1 and its ligands, PD-L1 and PD-L2. Pembrolizumab is an IgG4 kappa immunoglobulin with an approximate molecular weight of 149 kDa.

Pembrolizumab is supplied in two configurations: a “pembrolizumab for injection” configuration that is a single-use vial containing 50 mg lyophilized powder for reconstitution with 2.3 mL sterile water for injection resulting in a 25mg/mL solution (see [Section 6.2.3](#)) or “pembrolizumab injection” configuration that is a single-use vial containing pembrolizumab solution at a concentration of 100 mg/4mL (i.e., 25 mg/mL).

Pembrolizumab for injection is a sterile, preservative-free, white to off-white lyophilized powder in single-use vials. Each vial is reconstituted and diluted for intravenous infusion. Each 2 mL of reconstituted solution contains 50 mg of pembrolizumab and is formulated in

L-histidine (3.1 mg), polysorbate 80 (0.4 mg), and sucrose (140 mg). May contain hydrochloric acid/sodium hydroxide to adjust pH to 5.5.

Pembrolizumab injection is a sterile, preservative-free, clear to slightly opalescent, colorless to slightly yellow solution that requires dilution for IV infusion. Each vial contains 100 mg of pembrolizumab in 4 mL of solution. Each 1 mL of the 100 mg/4mL solution contains 25 mg of pembrolizumab and is formulated in: L-histidine (1.55 mg), polysorbate 80 (0.2 mg), sucrose (70 mg), and Water for Injection, USP. Pembrolizumab will be administered by IV infusion over 30 minutes through an IV line containing a sterile, non-pyrogenic, low-protein binding 0.2 micron to 5 micron in-line or add-on filter by IV infusion.

6.1.3 MGA012

MGA012 is

6.2 Drug Preparation

6.2.1 General Guidelines and Precautions

The calculated dose for MGA271 and pembrolizumab will be administered based on the patient's actual weight at Day 1. Significant ($\geq 10\%$) change in body weight from baseline should prompt recalculation of dose. Refer to the Pharmacy Manual for further instructions on allowable parameters for dose rounding of MGA271 and pembrolizumab.

For patients with weight > 120 kg, MGA271 dose calculations will be based on Ideal Body Weight (IBW) rather than actual weight using the following formula:

Estimated ideal body weight in (kg):

Males: IBW = 50 kg + 2.3 kg for each inch over 5 feet.

Females: IBW = 45.5 kg + 2.3 kg for each inch over 5 feet.

Infusion or allergic reactions may occur with the infusion of monoclonal antibodies and other protein-based therapeutics. Precautions for anaphylaxis should be observed during both MGA271 and pembrolizumab and MGA012 administration. Supportive measures may include, but are not limited to: epinephrine, antihistamines, corticosteroids, IV fluids, vasopressors, oxygen, bronchodilators, diphenhydramine, and acetaminophen. Please refer to **Section 6.5.1** for specific guidelines regarding the management of infusion reactions. Supportive care measures consistent with optimal patient care will be provided throughout the study according to institutional standards.

When both study drugs are administered on the same day, separate infusion bags must be used for each infusion. Pembrolizumab or MGA012 is to be administered first.

An effort should be made to begin the MGA271 infusion between 30 minutes to 120 minutes after the completion of the pembrolizumab or MGA012 infusion. It is understood that this window may not always be attainable, but is the preferred window of time to administer MGA271.

6.2.2 MGA271

- Inspect parenteral drug products visually for particulate matter and discoloration prior to administration. Some visible, proteinaceous MGA271 particles may be present. Discard vial if solution is cloudy, there is pronounced discoloration (), or there is foreign particulate matter.
- The desired amount of MGA271 should be withdrawn from the vial(s) and diluted to the appropriate final concentration with 0.9% Sodium Chloride Injection USP, according to the instructions provided in the Pharmacy Manual.
- The infusion bag containing MGA271 should be gently inverted to mix the solution. THE BAG MUST NOT BE SHAKEN; excessive agitation may cause aggregate formation. DO NOT FREEZE.
- Discard partially used vials of MGA271.
- Administration of study drug should begin immediately after preparation but

, to allow dose solution to reach room temperature. Precautions should be taken to minimize the time between dose preparation and IV infusion administration. If there is a delay in administration of study drug such that it will not be administered on the day of preparation, the Medical Monitor should be notified immediately. Instructions on how to proceed will be provided.

6.2.3 Pembrolizumab

Reconstitution instructions for pembrolizumab for injection lyophilized powder:

- Add 2.3 mL of Sterile Water for Injection, USP by injecting the water along the walls of the vial and not directly on the lyophilized powder (resulting concentration 25 mg/mL).
- Slowly swirl the vial. Allow up to 5 minutes for the bubbles to clear. Do not shake the vial.

Preparation for intravenous infusion:

- Visually inspect the reconstituted solution for particulate matter and discoloration prior to administration. The solution is clear to slightly opalescent, colorless to slightly yellow solution. Discard the vial of visible particulates are observed.
- Dilute pembrolizumab injection (solution) or reconstituted lyophilized powder prior to intravenous administration.
- Withdraw the required volume from the vial(s) of pembrolizumab and transfer into an IV bag containing 0.9% Sodium Chloride Injection, USP or 5% Dextrose Injection, USP. Mix diluted solution by gentle inversion. The final concentration of the diluted solution should be between 1 mg/mL to 10 mg/mL.
- Discard any unused portion left in the vial.

The product does not contain a preservative.

Store the reconstituted and diluted solutions from the pembrolizumab 50 mg vial either:

- At room temperature for no more than 6 hours from the time of reconstitution. This includes room temperature storage of reconstituted vials, storage of the infusion solution in the IV bag, and the duration of infusion.

Under refrigeration at 2°C to 8°C (36°F to 46°F) for no more than 24 hours from the time of reconstitution. If refrigerated, allow the diluted solution to come to room temperature prior to administration.

Do not freeze.

Store the diluted solution from the pembrolizumab 100 mg/4 mL vial either:

- At room temperature for no more than 6 hours from the time of reconstitution. This includes room temperature storage of the infusion solution in the IV bag, and the duration of infusion.
- Under refrigeration at 2°C to 8°C (36°F to 46°F) for no more than 24 hours from the time of dilution. If refrigerated, allow the diluted solution to come to room temperature prior to administration.
- Do not freeze.

6.2.4 MGA012

- Visual inspection of drug product vials for solution clarity, foreign particulate matter and discoloration is required prior to use. If solution cloudiness or foreign particulate matter or pronounced discoloration is observed (solution may have the drug product should not be used for dose preparation.

-

to allow dose solution to reach room temperature. Precautions should be taken to minimize the time between dose preparation and IV infusion administration.

- Instructions on the preparation of each study drug are detailed in the Pharmacy Manual. If there is a delay in administration of study drug such that it will not be administered on the day of preparation, the Medical Monitor should be notified immediately. Instructions on how to proceed will be provided.

6.2.5 Placebo or Control

There will be neither placebo nor active control drug for this study.

6.3 Study Drug Administration

6.3.1 MGA271

- Do not mix MGA271 with, or administer as an infusion with, other medicinal products.
- Administer the diluted solution over 120 minutes through an intravenous line using an infusion pump.
-
- Do NOT use non-polyolefin IV infusion bags.
- For cohorts with weekly MGA271 administration, an interval of at least 6 days should occur since the previous administration.
- For Cohort 4, MGA271 is administered Q3W \pm 3 days. An interval of at least 18 days should occur since the previous administration.
- MGA271 must not be administer as an IV push or bolus.

6.3.2 Pembrolizumab

- Administer infusion solution intravenously over 30 minutes through an intravenous line containing a sterile, non-pyrogenic, low-protein binding 0.2 micron to 5 micron in-line or add-on filter using an infusion pump.
- Do not co-administer other drugs through the same infusion line.
- Dose rounding within 10% of the originally calculated dose is allowed

6.3.3 MGA012

- MGA012 will be administered at a fixed dose of 375 mg, regardless of body weight or body surface area.
- All doses of MGA012 must be diluted in a 100-mL or 250-mL infusion bag containing 0.9% Sodium Chloride Injection, USP (normal saline), prior to dose administration. The dose solution should be administered over 60 to 75 minutes through an IV administration set with a commercially available infusion pump.
- Do not mix MGA012 with, or administer as an infusion with, other medicinal products. All IV infusions of MGA012 must be administered separately. Do not infuse MGA012 as an IV push or bolus.
- Study treatments are administered Q3W \pm 3 days. An interval of at least 18 days should occur since the previous administration.

6.4 Selection and Timing of Dose for Each Patient

Patients will be assigned to successive dose cohorts as described in [Section 4.1.2](#) and [Section 4.1.3](#).

6.5 Potential Adverse Events and Supportive Care Measures

6.5.1 Infusion Related Reactions Including Cytokine Release Syndrome

MGA271, pembrolizumab, and MGA012 are immune modulating agents that may lead to T-cell activation and killing of the tumor cell. Activation of T cells is associated with the production of various cytokines.

Infusion reactions (including cytokine release syndrome [CRS]) associated with either MGA271, pembrolizumab, or MGA012 administration should be managed according to the standard practice of medicine. General guidelines for the management of such reactions are provided in this section. However, severe reactions may require more intensive interventions (e.g., steroids, anti-TNF α antibodies, and/or IL-6 inhibitors).

Patients should be monitored closely for the development of infusion-related reactions during the pembrolizumab and MGA271 and MGA271+MGA012 infusions. Medications and supportive measures for the treatment of severe hypersensitivity reactions should be available for immediate use for an infusion reaction during study drug administration and may include, but are not limited to: subcutaneous (SC) epinephrine (0.3 to 0.5 mL of a 1:1000 solution), antihistamines (e.g., diphenhydramine 25 to 50 mg IV), corticosteroids (e.g., hydrocortisone 50-100 mg IV push or equivalent), IV fluids, vasopressors, oxygen, bronchodilators, and antipyretics. Resuscitation equipment and other supplies for the emergency management of

an allergic/toxic reaction must be available. The patient should be treated according to the best available local practices and procedures. All supportive measures consistent with optimal patient care will be provided throughout the study according to institutional standards.

Should symptoms of fever or chills develop it may be difficult to distinguish among potential causes of the symptoms including emerging infection, or infusion reaction. Patients should be evaluated carefully for the presence of infection, with the acquisition of cultures and/or implementation of empiric antibiotic therapy as appropriate based on the assessment of the Investigator. Please refer to **Section 6.5.1.3** for guidance regarding the management of infusion reactions.

If a patient has a Grade 1 or 2 infusion reaction with pembrolizumab or with MGA012 and the investigator considers it unsafe for the patient to receive MGA271 at the scheduled infusion time, the MGA271 dose may be administered on the following day (the day after the pembrolizumab infusion). For Grade 3 infusion reactions with pembrolizumab or with MGA012 that resolve completely or to Grade 1 within 12 hours, the scheduled dose of MGA271 may be administered the following day with premedications as listed below.

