- When both pembrolizumab and MGA271 or MGA012 and MGA271 are given on the same day and a patient has an infusion reaction with pembrolizumab or with MGA012:
 - The MGA271 infusion can be administered on the same day if the infusion reaction resolves within 3 hours. The MGA271 infusion may be given the next day if the infusion reaction last longer than 3 hours.
 - Premedication of diphenhydramine hydrochloride 25-50 mg IV and acetaminophen 650 mg orally should be administered 30 minutes prior to the MGA271 dose. If no corticosteroids were given for the pembrolizumab or

MGA012 infusion reaction, hydrocortisone 50-100 mg IV or equivalent may be considered prior to MGA271 administration.

- Prophylactic pre-infusion medications should be given prior to all subsequent pembrolizumab or MGA012 infusions. Patients who experience Grade 2 infusion reaction should be pre-medicated with diphenhydramine hydrochloride 25-50 mg IV and acetaminophen 650 mg orally for subsequent doses of pembrolizumab.
- If a patient has an infusion reaction with MGA271 on any of the days that it is administered after pembrolizumab or after MGA012, or given alone, prophylactic preinfusion medications should be given prior to all subsequent MGA271 infusions.
- For patients with Grade 2 infusion reactions despite premedication with diphenhydramine and acetaminophen, corticosteroids (hydrocortisone 50-100 mg IV or equivalent) should be considered for acute management of the event and should be added to the premedication regimen for subsequent dosing of pembrolizumab and/or MGA271 or subsequent dosing of MGA012 and/or MGA271.

Grade 3

- STOP THE INFUSION AND DISCONNECT THE INFUSION TUBING FROM THE PATIENT.
- TO AVOID EXACERBATION OF INFUSION REACTION OR CRS: DO NOT FLUSH THE TUBING – ASPIRATE RESIDUAL DRUG FROM THE PORT LUMEN.
- Administer diphenhydramine hydrochloride 25-50 mg IV, hydrocortisone 25-100 mg IV (or equivalent), and other medications/treatment as medically indicated. Higher doses of corticosteroids (i.e. methylprednisolone 2 -4 mg/kg IV) may also be considered for acute management.
- IV fluids, supplemental oxygen and bronchodilators should be considered as appropriate.

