- **Grade 3 infusion reaction with MGA271:** If symptoms have resolved to baseline within 12 hours, a re-challenge may be considered at the next scheduled dose, with a 50% reduction of infusion rate. In addition, patients should be pre-medicated for this re-challenge and for any subsequent doses of MGA271 with the following: diphenhydramine hydrochloride 25-50 mg IV, oral acetaminophen 625 mg and hydrocortisone 25-100 mg IV. Patients who have a Grade 3 infusion reaction that does not resolve within 12 hours despite medical management should not receive further MGA271, pembrolizumab, or MGA012 treatment.
- **Grade 3 infusion reaction with pembrolizumab or MGA012:** If the grade 3 infusion reaction occurs with pembrolizumab or with MGA012, both MGA271 and pembrolizumab or MGA271 and MGA012 will be discontinued for that day's dose. If symptoms have resolved to baseline within 12 hours, a pembrolizumab or

MGA012 re-challenge at the next scheduled infusion day may be considered, with a 50% reduction of infusion rate. In addition, patients should be pre-medicated for this re-challenge and for any subsequent doses of pembrolizumab or MGA012 with the following: diphenhydramine hydrochloride 25-50 mg IV, oral acetaminophen 625 mg and hydrocortisone 25-100 mg IV. MGA271 dosing can be resumed with at the next scheduled infusion day if the pembrolizumab or MGA012 grade 3 infusion reaction resolved to grade 1 within 12 hours. Patients who have a Grade 3 infusion reaction that does not resolve within 12 hours despite medical management should not receive further MGA271, pembrolizumab, or MGA012 treatment.

- Patients who experience a second Grade 3 infusion reaction at the time of re-challenge of MGA271 or pembrolizumab or MGA012 (irrespective of duration of first Grade 3 reaction), will permanently discontinue MGA271, and pembrolizumab and MGA012.
- Report as an Immediately Reportable Event (IRE) within 24 hours.
- Report the event as a SAE, if appropriate.

Grade 4

- STOP THE INFUSION AND DISCONNECT THE INFUSION TUBING FROM THE PATIENT.
- TO AVOID EXACERBATION OF INFUSION REACTION OR CRS: DO NOT FLUSH THE TUBING.
- Administer diphenhydramine hydrochloride 50 mg IV, methylprednisolone 2-4 mg/kg IV (or more as considered appropriate), and other medications/treatment as medically indicated (e.g., an IL-6 receptor inhibitor or IL-6 inhibitor, an IL-2 receptor inhibitor, and/or an anti-TNF α antibody).
- Give epinephrine or bronchodilators as indicated.

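### After a Grade 3 reaction to MGA012 or pembrolizumab that settles to Grade 1 within 12 hours, Protocol Sections 6.5.1 and 6.5.1.3 time MGA271 differently (Cohort 4: 1 day versus about 21 days)

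*Protocol*

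**What the plan says.** Two places in the protocol set the timing of MGA271 after a Grade 3 reaction to the anti-PD-1 antibody (pembrolizumab or MGA012), which is infused first.

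- **Section 6.5.1, last paragraph.** If the reaction resolves completely or to Grade 1 within 12 hours, "the scheduled dose of MGA271 may be administered the following day with premedications as listed below".
- **Section 6.5.1.3, Grade 3, bullet on pembrolizumab or MGA012.** When the reaction occurs, "both MGA271 and pembrolizumab or MGA271 and MGA012 will be discontinued for that day's dose". Later in the same bullet, "MGA271 dosing can be resumed with at the next scheduled infusion day if the pembrolizumab or MGA012 grade 3 infusion reaction resolved"; the required level is Grade 1, reached inside a 12-hour limit. The bullet also allows the anti-PD-1 drug to be tried again if symptoms returned to baseline within 12 hours: "MGA012 re-challenge at the next scheduled infusion day may be considered".

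Three other places bear on the reading.

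- The opening part of Section 6.5.1 refers the reader to Section 6.5.1.3 "for guidance regarding the management of infusion reactions".
- Footnote 1 of the Cohort 4 schedule in Appendix 1 allows MGA271 on the next day for safety or scheduling reasons, without naming a reaction grade.
- Section 6.5.1 describes its content as general guidelines, and Section 6.5.1.3 lets the investigator modify its guidelines.

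**The concern.** The drug that caused the reaction, its grade and the 12-hour limit are the same in both places, yet the MGA271 timing differs. One section keeps the scheduled dose and allows it a day later. The other does not give it at that visit and allows MGA271 from the next dosing visit.

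What is at stake is whether a second antibody may be given one day after a severe reaction to the first. Two Cohort 4 sites could handle the same event differently, and each could point to protocol text. The safety report does not close the gap. The Grade 3 instructions say "Report as an Immediately Reportable Event (IRE) within 24 hours", and a report made within that limit could still reach the sponsor after a next-day dose.

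**Working it through.** No sample size, power or error-rate figure is involved. The check compares the two texts and counts days on the protocol's own schedule.

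**1. Do the two rules cover the same event?**

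| | Section 6.5.1 | Section 6.5.1.3, Grade 3 |
|---|---|---|
| Drug causing the reaction | pembrolizumab or MGA012 | pembrolizumab or MGA012 |
| Grade | 3 | 3 |
| Condition for MGA271 | resolved completely or to Grade 1 within 12 h | resolved to Grade 1 within 12 h |
| MGA271 timing | following day | next scheduled infusion day |

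The conditions are not word for word the same, but a reaction that settles to Grade 1 within 12 hours meets both.

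**2. Could the two timings mean the same thing?** The clause on that day's dose could be read alone as barring only same-day MGA271, which would leave the following day open. The conflict therefore rests on the resumption clause. Three points show that its timing is not the next calendar day.

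- The same bullet uses the same phrase for re-challenge with MGA012, and Section 6.3.3 says of that drug: "An interval of at least 18 days should occur since the previous administration". For MGA012 the phrase cannot mean tomorrow.
- Where Section 6.5.1.3 means the next calendar day, it says so. Under Grade 2: "The MGA271 infusion may be given the next day if the infusion reaction last longer than 3 hours". The Grade 1 text does likewise. The Grade 3 bullet uses different words.
- In Section 6.5.1, the sentence just before the Grade 3 rule uses the same expression for Grade 1 or 2 reactions and explains it as the day after the pembrolizumab infusion.

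**3. How far apart are the timings in Cohort 4?**

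Inputs: MGA271 is given every 3 weeks, ±3 days, at least 18 days apart (Section 6.3.1). Infusion days are Days 1 and 22 of Cycle 1 and Days 1, 22 and 43 of later cycles (Table 9). Cycle 1 lasts 6 weeks, so Cycle 2 Day 1 is Study Day 43. The schedule agrees with itself: 21 − 3 = 18 days, the stated minimum.

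*Reaction on Cycle 1 Day 1:*
- Section 6.5.1: MGA271 on Day 2, and 2 − 1 = **1 day**.
- Section 6.5.1.3: MGA271 on Day 22, and 22 − 1 = **21 days**. With the window, 21 − 3 = 18 to 21 + 3 = 24 days.
- Feasibility of the next-day route: from Day 2 to Day 22 is 22 − 2 = 20 days, above the 18-day minimum. The dosing interval does not rule it out, so a site could follow either text.

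*Reaction on Cycle 1 Day 22:* Day 23 (23 − 22 = 1 day) against Study Day 43 (43 − 22 = 21 days). The same 21-day step applies between infusion days in later cycles.

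**4. Weekly cohorts, for comparison.** With weekly MGA271 (at least 6 days apart, Section 6.3.1), the contrast would be 1 day against about 7. Section 2.3.1.1.2 reports that patients in the pembrolizumab cohorts have completed combination treatment, so this contrast no longer has practical effect.

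**5. Does any text decide between the sections?** None does. The referral to Section 6.5.1.3 closes a paragraph on telling infection from infusion reaction when fever or chills develop, and it does not say that one section overrides the other. Footnote 1 allows next-day MGA271 in general terms and does not address Grade 3 reactions.

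**The case against.** The strongest reply is that both resumption clauses only permit. A site that waits for the next scheduled visit breaches neither section, so the only open question is whether the next-day option survives. The investigator may also modify the guidance. This stands, and it is why the point is narrow. It does not remove the conflict: withholding that day's dose is not worded as an option, and discretion does not explain why one severe event has two different default instructions.

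A second reply is that footnote 1, and its counterpart in the pembrolizumab schedule, also allow next-day MGA271, and a reaction to MGA012 is plainly a safety reason. The Grade 3 bullet may then simply be a drafting slip. That is possible, but the footnotes name no grade and the bullet is the only text in the detailed Grade 3 instructions that times MGA271 after an anti-PD-1 reaction. A site cannot tell from the protocol which text is the slip.

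Third, the resumption clause has a stray word and may have lost something. The timing phrase is intact, so the conflict remains, although a further condition on resumption may be missing.

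Fourth, Section 4.5.1 has its own rules: a 14-day limit on toxicity interruptions, an allowance in Cohort 4 of one dose of each drug, and provision for a full complement of doses. The 18-to-24-day figure is therefore the timing under Section 6.5.1.3 and the dosing schedule, not a full account of what a site would do. Section 4.5.1 does not choose between the two timings.

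Finally, reach is limited. Cohort 4 may have up to 15 dose-evaluable patients at this dose level, and the documents do not say whether any are still being dosed.

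**Conclusion.** The inconsistency is real. For the same Grade 3 event, the protocol permits MGA271 after 1 day in one section and after about 21 days (18 to 24 with the window) in another for Cohort 4, and no text gives either precedence. It should be fixed because it concerns safety and costs little to correct.

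The conclusion rests on reading the next scheduled infusion day as the next protocol dosing visit, which the bullet's own use of the phrase for MGA012 supports. It also takes the Cohort 4 schedule as written.

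Frequency is unknown. The documents give no rate of Grade 3 MGA012 infusion reactions that resolve within 12 hours, so none is estimated. No endpoint, estimate or dose-escalation threshold is shown to change. Whether a Cohort 4 patient whose Day 1 MGA271 is withheld remains evaluable for DLT is a separate question that this point does not settle, and no effect on DLT counts is claimed.

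**What to change.** Reconcile Section 6.5.1 with the Grade 3 part of Section 6.5.1.3 so that one instruction governs MGA271 timing after a Grade 3 pembrolizumab or MGA012 reaction that resolves within 12 hours. Use the same definition of resolution in both places and repair the damaged resumption clause. Align footnote 1 of the Cohort 4 schedule in Appendix 1, for example by having it refer to that instruction after a reaction. The clinical team chooses the rule.

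The cost is a protocol clarification and a memo to Cohort 4 sites. No patients, visits or procedures are added.
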